In Period 2, a single cohort of up to 8 healthy participants including up to 6 WVE-006 and up to 2 placebo treated participants (3:1 active:placebo) will participate in a multidose cohort of WVE-006. The DEC and DMC will review available safety and PK data from Period 1 to select the maximum tolerated dose level (MTD) with an acceptable PK profile. The MTD is defined as the dose below a dose level where any of the dose escalation stopping rules were met. If the MTD is not achieved in Period 1 (i.e., no dose escalation stopping rules were met and all doses were well tolerated), then the highest dose reached in Period 1 will likely be selected for Period 2. The DEC and DMC may select a lower dose based on all available information. At least 4 weeks of safety data for the proposed dose and all available data from the study must be available from Period 1 in order to inform the DEC and DMC Period 2 dose selection. A sentinel strategy will be employed for the first 2 participants

Sponsor:	Investigational Product:	Developmental Phase:	IRAS ID Number:
Wave Life Sciences UK Limited	WVE-006	Phase 1	1008635

(1 active:1 placebo) during the multiple dose portion of the study. The sentinel participants will be dosed and monitored in the clinic for a minimum of 48 hours to identify any potential acute safety events. If neither of these sentinel participants experiences stopping criteria and if there are no other safety concerns during this 48-hour period, the remaining 6 participants will be randomized in a blinded fashion to active study drug (n=5) or placebo (n=1) and may be dosed on the same day. WVE-006 or placebo will be administered every other week (Q2W) over 4 weeks (total of 3 doses; Weeks 0, 2, and 4). Following the first dose (Week 0) and last dose (Week 4), all participants will stay in the clinic for two nights for PK assessments. Following the second dose (Week 2), all participants will be observed for safety evaluation in the clinic for at least 4 hours post-study drug administration or per local SOP (whichever is longer). All participants will attend weekly follow-up clinic visits for safety, tolerability, and PK assessments through Week 12 followed by visits every 4 weeks through week 16 or early termination visit.

Dose Escalation Stopping Criteria (Period 1):

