Dose escalation will be paused until further evaluation by the DMC if any of the following criteria are met. If it is confirmed that a stopping criterion was met, no further dosing will take place until after submission and approval of a substantial amendment if the DMC recommends the trial can continue.

- One or more participants experiencing at least possibly related Common Terminology Criteria for Adverse Events (CTCAE) Grade ≥ 3 TEAE or CTCAE grade ≥ 3 laboratory abnormality in a single cohort.
 - All grade 3 toxicities for vital signs must be confirmed with a repeat measurement obtained within 1 hour.
 - All grade 3 toxicities for laboratory parameters must be confirmed with a repeat measurement obtained within 24 hours.
- Two or more participants experiencing at least possibly related CTCAE grade ≥ 2 TEAEs or CTCAE Grade ≥ 2 laboratory abnormalities in a single cohort.
 - All grade 2 toxicities for vital signs must be confirmed with a repeat measurement obtained within 1 hour.
 - All grade 2 toxicities for laboratory parameters must be confirmed with a repeat measurement obtained within 24 hours.
- One or more participants experiencing any at least possibly related SAE in a single cohort.

Period 2 Individual Stopping Criteria:

Dosing will be paused or discontinued (per Investigator judgment) for an individual participant at any time in the study if:

- Participant experiences any severe or serious adverse event considered at least possibly related to study drug.
- Participant experiences, in the Investigator's opinion, clinically significant hypersensitivity to WVE-006 (or placebo) administration.
- Participant has any medical condition that is judged by the Investigator to jeopardize the participant's safety if he or she continues to receive the study drug.

On discontinuation of treatment, participants will be encouraged to continue follow-up for safety per protocol. Per Investigator judgment with consultation with the Sponsor, the participant may be allowed to resume participation in the study if/when the event has resolved.

Sponsor: Wave Life Sciences UK Limited	Investigational Product: WVE-006	Developmental Phase: Phase 1	IRAS ID Number: 1008635

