4.1.4 Early Termination

If a participant withdraws from the study early, the participant should complete an early termination (ET) visit. Assessments to be performed at the ET visit are detailed in [Table 1](#) for Period 1 and [Table 5](#) for Period 2. Refer to [Section 7](#) for information on early withdrawal from study drug or from the study.

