4.4 End of Study Definition

The end of the study is defined as the date of the last visit of the last participant in the study.

A participant is considered to have completed the study if the participant has completed all study visits including Week 12 for Period 1, Week 16 for Period 2, or the ET visit.

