6.1 Study Drugs Administered

Study drugs include WVE-006 and placebo. Details on study drugs are provided in [Table 9](#).

Table 9 Study Drugs Administered

Study Drug Label	WVE-006	Placebo
Study Drug Name	WVE-006	Placebo
Study Drug Description	Period 1: SC injection, one dose per participant at varying dose levels. Period 2: SC injection, Q2W at a dose level identified in Period 1.	Period 1: SC injection, once per participant. Period 2: SC injection, Q2W.
Type	Drug	Drug
Dose Formulation	Lyophilized powder for reconstitution	0.9% normal saline, sterile solution for injection
Unit Dose Strengths	CCI per vial	N/A
Dosage Levels	Period 1: single dose Starting Dose: 30 mg Highest dose: see Section 4.1.2 Period 2: Q2W dosing for a total of 3 doses at the dose level selected from Period 1	N/A (same volume as corresponding WVE-006 dose)
Route of Administration	SC injection	SC injection
Use	Experimental	Placebo
Sourcing	Provided centrally by the Sponsor	Provided locally by the site
Packaging and Labeling	Study drug will be provided in 10 mL single use vial. Each vial will be labeled as required per country requirement.	N/A

Abbreviations: SC = subcutaneous; Q2W = every other week

Table 10 Study Periods

Period Title	Period 1	Period 2
Period Type	Single ascending dose	Multiple dose
Period Description	Participants will receive WVE-006 or placebo once SC starting at 30 mg and escalating as per the study schema.	Participants will receive a total of 3 doses of WVE-006 or placebo Q2W SC at the MTD, highest dose, or other selected dose

	Participants will be followed for 12 weeks.	from Period 1. Participants will be followed for 12 weeks following last study drug administration.
Associated Study Drug Labels	WVE-006, Placebo	WVE-006, Placebo

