6.5 Blinding

In order to maintain the blinding of the study drug (WVE-006 or placebo), all study personnel will be blinded to participant treatment assignment. Physicians, nurses, participants, contract research organization (CRO) staff, and any study personnel performing participant assessments must NOT be informed of the participant's treatment assignment (see Study Manual) except if unblinding is required or as required by regulatory authorities ([Section 6.5.1](#)).

The pharmacy personnel will be unblinded to prepare doses of study drug to ensure that the clinical site staff responsible for administering study drug and conducting assessments per the protocol, and the participant remain blinded to study treatment. In addition, a clinical research associate will be unblinded to perform drug accountability.

6.5.1 *Breaking the Blind*

6.5.1.1 *Unblinding In Case Knowledge of Treatment May Impact Medical Management*

To maintain the overall quality of data collected during the study, breaks in blinding during the conduct of the study should occur only in exceptional circumstances when knowledge of the actual treatment is essential for further management of the participant. Unblinding of the study drug for an individual can be done during the study period in the case of:

- Any AE where knowledge of the treatment assignment is deemed necessary to treat the participant
- Pregnancy of a participant or participant's partner in the study

Procedures for unblinding will be described in a Study Manual supplied to the site. The investigator should make every effort to contact the Sponsor's Medical Monitor before unblinding a participant's treatment assignment unless this could delay emergency treatment of the participant. In all circumstances other than a medical emergency, unblinding will be done only after discussion with the Sponsor's Medical Monitor. Emergency treatment unblinding must be reported to the Sponsor's Medical Monitor immediately. When it is necessary to break the blind, the investigator must notify the Ethics Committee (EC)/Institutional Review Board (IRB) as applicable. If a participant is unblinded, the participant will discontinue further treatment with study drug (i.e., MD) and will have either a routine scheduled visit if due or an unscheduled visit as soon as possible to evaluate the safety concern that prompted the unblinding.

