7 DISCONTINUATION OF STUDY DRUG AND PARTICIPANT DISCONTINUATION/WITHDRAWAL

Participants are free to withdraw from the study or discontinue study treatment at any time upon request without prejudice to their future medical care by the Investigator or at the study site. Participation in the study may also be stopped at any time at the discretion of the Investigator or at the request of the Sponsor. Participants who withdraw or discontinue from study treatment will no longer receive investigational drug.

7.1 Discontinuation of Study Treatment in Period 2

A participant must permanently discontinue study treatment for any of the following:

- The participant is withdrawn from the study ([Section 7.1.2](#)).
- The participant experiences an AE that in the Investigator's opinion requires treatment discontinuation.
- A change in the participant's medical condition not consistent with the protocol requirements or that justifies discontinuation of study drug.
- Pregnancy (refer to [Section 10.3.6](#)).

If a participant discontinues treatment, they will be encouraged to complete the ET visit, unless consent is withdrawn.

The reason for discontinuation of study treatment must be recorded in the eCRF and source documentation.

7.1.1 *Period 2 Individual Stopping Criteria:*

Dosing will be paused or discontinued (per Investigator judgment) for an individual participant at any time in the study if:

- Participant experiences any severe event or SAE considered at least possibly related to study drug.
- Participant experiences clinically significant hypersensitivity to WVE-006 (or placebo) administration.
- Participant has any medical condition that is judged by the Investigator to jeopardize the participant's safety if he or she continues to receive the study drug.

7.1.2 *Withdrawal of Participants from the Study*

Participants must be withdrawn from the study for any of the following:

- The participant withdraws consent
 - At the discretion of the Investigator for medical reasons
-

- At the discretion of the Investigator or Sponsor for noncompliance
- Major protocol deviation that may impact interpretation of data (after discussion with Sponsor) (see [Section 10.5.2](#))
- Termination of the study by the Sponsor (see [Section 10.1.9](#))
- At the discretion of the Sponsor for any reason

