10.3.2 Time Period and Frequency for Collecting AE and SAE Information

AEs and SAEs will be collected beginning with the signing of the ICF until the last study visit or ET visit.

Medical occurrences that begin before the start of study drug but continue after obtaining informed consent will be recorded as medical history/current medical conditions, not as AEs unless the condition has worsened in terms of severity or frequency.

Investigators are not obligated to actively seek information on AEs after conclusion of study participation. SAEs that occur after the final follow-up visit need not be reported unless the Investigator considers them at least possibly related to study drug. However, if the Investigator learns of any pregnancy within a month after a participant completed or was discharged from the study, the Investigator must promptly notify the Sponsor (see [Section 10.3.6](#)).

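### For a Period 2 participant who stops study treatment, the synopsis continues safety follow-up, but Section 7.1 names only the early termination visit, which elsewhere marks the end of participation

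*Combined protocol and SAP*

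**What the plan says.** **After treatment is discontinued in Period 2.** The synopsis, under the Period 2 individual stopping criteria, says: "On discontinuation of treatment, participants will be encouraged to continue follow-up for safety per protocol". Section 7.1 says: "If a participant discontinues treatment, they will be encouraged to complete the ET visit, unless consent is withdrawn". Section 7.1.1 repeats the three individual stopping criteria but leaves out the synopsis sentence on continued follow-up.

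**What the ET visit is.**
- Section 4.1.4: "If a participant withdraws from the study early, the participant should complete an early termination (ET) visit". The same section refers to Section 7 for stopping study drug as well as for leaving the study.
- Section 4.4 counts a participant as having completed the study who "has completed all study visits including Week 12 for Period 1, Week 16 for Period 2, or the ET visit".
- The synopsis describes the end of the Period 2 visits as weekly visits to Week 12, "followed by visits every 4 weeks through week 16 or early termination visit".
- Section 10.3.2: "AEs and SAEs will be collected beginning with the signing of the ICF until the last study visit or ET visit".

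**How long follow-up is meant to last.** For Period 2, Table 10 in Section 6.1 says: "Participants will be followed for 12 weeks following last study drug administration". The overall design text in the synopsis likewise sets safety evaluation in both periods through Day 85 counted from the last dose. Neither statement mentions participants who stop treatment early. Section 4.1.3 describes follow-up after treatment has been completed.

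**The concern.** Both instructions apply to the same event, and they point to different visits. If the ET visit were simply one more safety visit, the difference would be trivial. But Sections 4.4 and 10.3.2 and the synopsis set it beside the final visit as the place where participation or adverse event collection ends. A site reading Section 7.1 with those sections could arrange an ET visit, record the participant as complete, and stop looking for new events.

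The participants concerned are those stopped for a severe or serious event judged possibly related to study drug, for clinically significant hypersensitivity, or for another medical reason. In a cohort with at most 6 participants on active drug, they carry much of the information for the primary safety objective. Section 9.3.5.1 ends the treatment-emergent window at study completion or discontinuation. The choice between the two instructions therefore also changes how long primary-endpoint events are counted.

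**Working it through.** The protocol states no figure to reproduce. The check sets the texts side by side and then counts what could be lost.

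**1. Do the body sections settle the matter?**

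| Place | What it covers | Settles it? |
|---|---|---|
| Synopsis, stopping criteria | Treatment discontinued: continue safety follow-up | Yes, but not repeated in Section 7 |
| Section 7.1 | Treatment discontinued: ET visit | Silent on later visits |
| Section 7.1.1 | Stopping criteria only | No |
| Section 4.1.3 | After completed treatment | No |
| Section 7.2 | A dose that cannot be given at a visit | No; concerns a missed dose |
| Synopsis overall design; Table 10 | 12 weeks after last dose, generally | Supports the synopsis; does not mention discontinuation |

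No body section says that a participant who has discontinued treatment stays on the Table 5 schedule.

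**2. Planned length of follow-up.** The last dose is on Day 29 and the last visit on Day 113, so 113 − 29 = 84 days, or 12 weeks. This matches the protocol's Day 85 counted from the last dose.

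**3. Visits at stake, from Table 5 (nominal days, windows ignored).**
- *After dose 1 (Day 1).* Twelve weeks ends on Day 1 + 84 = Day 85, which is a scheduled visit. Remaining visits are Days 8, 15, 21, 29, 36, 43, 50, 57, 64, 71, 78 and 85, which makes 12.
- *After dose 2 (Day 15).* Twelve weeks ends on Day 15 + 84 = Day 99, which is not a scheduled visit. Day 85 is only 85 − 15 = 70 days after dose 2. The first scheduled visit to reach 12 weeks is Day 113, at 113 − 15 = 98 days. Remaining visits are Days 21, 29, 36, 43, 50, 57, 64, 71, 78, 85 and 113, which makes 11.

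The protocol does not date the ET visit. The possible loss therefore runs from 0 visits (the site keeps to the schedule) to 12 or 11 (the ET visit comes before the next scheduled visit and ends follow-up).

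**4. One illustration between the extremes.** Assume the ET visit falls at the next dosing visit and ends follow-up. After dose 1 that gives 15 − 1 = 14 days; after dose 2 it gives 29 − 15 = 14 days. In both cases 84 − 14 = 70 of the 84 planned days are lost, or 83%.

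**5. Data due at those visits.** Adverse event monitoring is due at all of them. Table 6 places the blood count, CRP, fibrinogen, coagulation and albumin panel at every visit. ECGs still ahead include Days 57 and 85, and also Day 113 after two doses. For plasma PK, Section 7.2 does not require samples at a visit where the participant cannot be dosed. If that is applied to a discontinued participant, the PK visits at stake are 12 − 2 = 10 after dose 1 (Days 15 and 29 drop out) and 11 − 1 = 10 after dose 2 (Day 29 drops out).

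**The case against.** The strongest reply is that the two sentences are compatible. Each only encourages something, and neither excludes the other. A site would have to read Section 7.1 in isolation, setting aside the synopsis, Table 10 and the general rule tied to the last dose. Section 10.3.2 offers alternatives, so a participant who stays on schedule has a last study visit. Section 10.3 also collects adverse events to the end of the study. The event that caused stopping is not lost either: Section 10.3 follows ongoing adverse events, and Section 10.3.5.3 follows serious ones, to resolution or stabilization.

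Most of this stands, and it limits the point. It shows that loss is not certain and that what is exposed is new events and scheduled laboratory and ECG data. It does not remove the divergence. The operative section still names only a visit that other sections use to close participation, and the synopsis sentence that would correct this is missing from Section 7.

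A reader might infer more than the documents support:
- **That Section 7.1 requires follow-up to end.** It does not; it is silent on later visits. Section 4.1.4 does not strictly reserve the ET visit for leaving the study either, since it also refers to stopping study drug.
- **That Section 6.5.1.1 adds a third rule.** After unblinding a participant stops treatment "and will have either a routine scheduled visit if due or an unscheduled visit as soon as possible". That visit is an immediate check of the safety concern behind the unblinding and says nothing about later follow-up.
- **That the synopsis allows a permanently discontinued participant to be dosed again.** Its sentence on resuming speaks of participation, not dosing, and follows a lead-in covering both paused and discontinued dosing. Section 7 says discontinued participants receive no more drug. The wording is ambiguous, not contradictory.
- **That the restart test in Section 7.2 is too narrow because it names only a skipped second dose.** With three doses, that is essentially the only restart that can arise: a skipped third dose leaves nothing to restart.
- **That 13 visits are at stake after dose 1.** That count includes Day 113, which lies beyond 12 weeks after a single dose.

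**Conclusion.** The point holds as an inconsistency between the synopsis and Section 7.1, with possible rather than certain loss of primary-endpoint safety data. The size is 0 to 12 scheduled visits for a participant stopped after dose 1 and 0 to 11 after dose 2. It applies only to those who discontinue among at most 8 Period 2 participants.

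These counts rest on three assumptions: nominal visit days, 12 weeks after the last dose as the intended follow-up, and, for the upper ends, a site that holds the ET visit before the next scheduled visit and treats it as final. The documents do not fix the date of the ET visit, so no single figure can be given.

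The impact is narrow. Correction is still worthwhile because the participants affected are the most informative for safety and the remedy is a matter of wording.

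**What to change.** In Section 7.1, replace the ET-visit sentence with: *A participant who discontinues treatment will be encouraged to continue the scheduled Table 5 safety visits for at least 12 weeks after the last dose received (through the Day 85 visit after one dose, through the Day 113 visit after two or three); the ET visit is done only if the participant leaves the study before then.* Repeat the follow-up sentence in Section 7.1.1.

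Two clerical clarifications can go in at the same time. In the synopsis, say that resuming dosing applies only to a participant whose dosing was paused. In Section 6.7, the reference for dose changes due to adverse events points to Section 7.1.2, which contains no dose rule; redirect it to Sections 7.1.1 and 7.2.

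The cost is wording only, with no additional participants, visits or procedures. The Day 85 and Day 113 visits are already in Table 5, and Section 7.2 already runs visits without dosing. Using Day 113 after two doses gives 98 days rather than 84, which avoids creating a new Day 99 visit.

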1.2 Protocol Schema

1.3 Schedule of Assessments**Table 1 Overall Schedule of Assessments (Period 1)**

	Screening Period ^a	Dosing- CRU Stay				Follow-up				ET
Visit	1	2				3, 4, 5, 7, 8, 9, 11, 12, 13	6	10	14	
Study Week	Week -4 to Week 0	Week 0				Week 1, 2, 3, 5, 6, 7, 9, 10, 11	Week 4	Week 8	Week 12	
Study Day Event/Assessment	Day -28 to Day -2	Day -1	Day 1	Day 2	Day 3	Day 8, 15, 22, 36, 43, 50, 64, 71, 78 (±3 days)	Day 29 (±3 days)	Day 57 (±3 days)	Day 85 (±5 days)	
Informed Consent	X									
Demographics	X									
Medical History	X									
Prior/concomitant medications	X	X	X	X	X	X	X	X	X	X
Admission to CRU		X								
Discharge from CRU					X					
Eligibility Criteria/Recheck	X	X								
AAT Genetic Testing	X									
Serum Pregnancy Test ^b	X								X	X
Urine Pregnancy Test ^b		X			X	X	X	X		
FSH ^c	X									
Viral Serology	X									
COVID-19 Testing ^d	X	X								

	Screening Period ^a	Dosing- CRU Stay				Follow-up				ET
Visit	1	2				3, 4, 5, 7, 8, 9, 11, 12, 13	6	10	14	
Study Week	Week -4 to Week 0	Week 0				Week 1, 2, 3, 5, 6, 7, 9, 10, 11	Week 4	Week 8	Week 12	
Study Day Event/Assessment	Day -28 to Day -2	Day -1	Day 1	Day 2	Day 3	Day 8, 15, 22, 36, 43, 50, 64, 71, 78 (±3 days)	Day 29 (±3 days)	Day 57 (±3 days)	Day 85 (±5 days)	
Safety Laboratory ^c	X	X		X	X	X	X	X	X	X
Plasma PK and Select Labs ^f			X	X	X	X	X	X	X	X
Urine PK sample ^f			X	X	X	X	X	X	X	X
Serum Sample for Immunogenicity		X					X	X	X	X
Full Physical Exam ^g	X	X			X		X	X	X	X
Symptom-directed Physical Exam ^g			X	X		X				
Body Weight/BMI ^h	X	X		X	X	X	X	X	X	X
Height	X									
Vital Signs ⁱ	X	X	X	X	X	X	X	X	X	X
Digital Continuous and Triplicate 12-lead ECG ^j	X	X		X	X				X	X
Urine Drug Screen ^k ; Cotinine; Alcohol Breath or Urine Test	X	X				X	X	X	X	X
Study Drug Administration SC Injection			X							

	Screening Period ^a	Dosing- CRU Stay				Follow-up				ET
Visit	1	2				3, 4, 5, 7, 8, 9, 11, 12, 13	6	10	14	
Study Week	Week -4 to Week 0	Week 0				Week 1, 2, 3, 5, 6, 7, 9, 10, 11	Week 4	Week 8	Week 12	
Study Day Event/Assessment	Day -28 to Day -2	Day -1	Day 1	Day 2	Day 3	Day 8, 15, 22, 36, 43, 50, 64, 71, 78 (±3 days)	Day 29 (±3 days)	Day 57 (±3 days)	Day 85 (±5 days)	
Adverse Event Monitoring	X	X	X	X	X	X	X	X	X	X

Abbreviations: AAT = alpha-1 antitrypsin; BMI = body mass index; CRU = clinical research unit; ECG = electrocardiogram; ET = early termination; FSH = follicle stimulating hormone; PK = pharmacokinetic; SC = subcutaneous.

^a Screening assessments can occur on multiple days, provided they are within the Day -28 up to Day -2 Screening period.

^b Negative serum pregnancy test at Screening for women of childbearing potential (WOCBP). Negative highly sensitive urine pregnancy test documented for WOCBP on Day -1.

^c FSH only to confirm non-childbearing potential.

^d COVID-19 testing if required per site SOPs.

^e Safety laboratory tests include hematology, clinical chemistry, coagulation and urinalysis as noted in [Table 11](#). Note that for urinalysis, abnormal results on dipstick or urinalysis should lead to laboratory urinalysis testing and/or urine microscopy. Any specific safety labs indicated in [Table 2](#) will be collected according to the schedule in that table. When applicable and feasible, blood sampling should follow evaluations of vital signs and ECGs to reduce any impact on these measurements.

^f Specific time points for PK and select laboratory assessments provided in [Table 2](#) and [Table 3](#). Participants should stay in the clinic for 48 hours after dose to complete assessments.

^g Full physical examination includes (at a minimum): alertness and orientation, general appearance, skin, head, eyes, ears, nose, throat, lungs, cardiovascular, gastrointestinal, musculoskeletal, and neurologic systems. Symptom-directed physical exams to be performed by visit as necessary.

^h Height at Screening will be used for BMI calculations at all visits.

ⁱ Vital signs will be taken with the participant in the supine position after ≥5 minutes of rest. Temperature, respiratory rate, and percent oxygen saturation in the blood (SpO₂) are measured once per time point. Blood pressure (systolic and diastolic) and pulse: measured ≤30 minutes pre-dose and 1 hr (±10 min), 2 hr (±10 min), 4 hr (±20 min), 12 hr (±1 hr) post dose on Day 1 and once at all other noted visits.

^j Continuous digital ECG monitoring for at least 48 hours from Day -1 through Day 2; leads may be disconnected for ~20 minutes at 24 hours after dosing to allow for participant cleansing. Additional triplicate 12-lead ECGs are specified in [Table 4](#). Participant must rest quietly for ≥5 minutes prior to triplicate ECGs.

^k For drug screen panel, see [Table 11](#) other screening tests.

Table 2 Plasma PK and Selected Laboratory Time Points (Period 1)

Visit	2											3	4	5 through 14
Study Day/ Specific Time/ Window	Day 1								Day 2		Day 3	Day 8	Day 15	Weeks 3 through 12
	Pre-dose	Post dose												
	≤30 min prior to dose ^b	30 min (±5 min)	1 hr (±5 min)	2 hr (±5 min)	4 hr (±10 min)	6 hr (±10 min)	8 hr (±10 min)	12 hr (±10 min)	24 hr (±30 min)	36 hr (±4 hr)	48 hr (±4 hr)	(±3 days)	(±3 days)	(± 3 days)
Plasma PK ^a	X	X	X	X	X	X	X	X	X	X	X	X	X	Every week
CBC, CRP, fibrinogen, coagulation, albumin	X					X			X		X	X	X	Every week
Complement	X			X	X	X			X		X	X	X	Week 4 only
Cytokines ^c	X			X	X	X			X		X	X	X	Week 4 only

Abbreviations: CBC = complete blood count; CRP = C-reactive protein; PK = pharmacokinetic.

^a Sufficient plasma PK sample volume to cover both WVE-006 and potential metabolites. When applicable and feasible, PK blood sampling should follow evaluations of vital signs and ECGs to reduce any impact on these measurements.

^b Pre-dose laboratory results are NOT required prior to dosing.

^c Cytokine samples will be collected and may be analyzed for the following cytokines: IL-1β, IL-6, IL-10, IL-12/23 (P40), IFN-γ, TNF-α, MCP-1, and MIP-1β

Table 3 Urine PK Cumulative Collection Periods (Period 1)

Study Day/ Time Frame	Day 1					Day 2	Day 3
	0-4 hr	4-8 hr	8-12 hr	12-18 hr	18-24 hr	24-36 hr	36-48 hr
Urine PK ^a	X	X	X	X	X	X	X

Abbreviation: PK = pharmacokinetic.

^a Urine for PK assessments will be collected continuously through 48 hours per the stated time periods. For each of these time periods, total volume will be captured in the electronic case report form (eCRF).

Table 4 Triplicate ECG Assessment Time Points (Period 1)

Study Day/ Specific Time	Day 1											Day 2	Day 3
	Pre-dose			Post dose									
	-45 min ±5 min	-30 min ±5 min	-15 min ±5 min	30 min ±5 min	1 hr ±5 min	2 hr ±5 min	4hr ±10 min	6hr ±10 min	8hr ±10 min	12hr ±10 min	24hr ±30 min	48hr ±4 hr	
ECG ^a	X	X	X	X	X	X	X	X	X	X	X	X	X

Abbreviations: ECG = electrocardiogram

^a Digital ECG monitoring for at least 48 hours from Day -1 through Day 2. Additional triplicate ECG measurements at the time points listed here.**Table 5 Overall Schedule of Assessments (Period 2)**

	Screening Period ^a	Treatment Period								Follow-up Visit				ET
Visit	1	2				4	6			3, 5, 7, 8, 9, 11, 12, 13, 14, 15, 16	10	14	15	
Study Week	Week -4 to Week 0	Week 0 CRU Stay				Week 2	Week 4 CRU Stay			Week 1,3, 5, 6, 7, 9, 10, 11	Week 8	Week 12	Week 16	
Study Day/ Event/ Assessment	Day -28 to Day -2	Day -1	Day 1	Day 2	Day 3	Day 15 (±3 days)	Day 29 (±3 days)	Day 30 (±3 days)	Day 31 (±3 days)	Day 8, 21, 36, 43, 50, 64, 71, 78 (±3 days)	Day 57 (±3 days)	Day 85 (±3 days)	Day 113 (±5 days)	
Informed Consent	X													
Demographics	X													
Medical History	X													
Prior/concomitant medications	X	X	X	X	X	X	X	X	X	X	X	X	X	X
Admission to CRU		X				X ^b	X ^b							
Discharge from CRU					X	X			X					

[illegible]

	Screening Period ^a	Treatment Period								Follow-up Visit				ET
Visit	1	2				4	6			3, 5, 7, 8, 9, 11, 12, 13, 14, 15, 16	10	14	15	
Study Week	Week -4 to Week 0	Week 0 CRU Stay				Week 2	Week 4 CRU Stay			Week 1, 3, 5, 6, 7, 9, 10, 11	Week 8	Week 12	Week 16	
Study Day/ Event/ Assessment	Day -28 to Day -2	Day -1	Day 1	Day 2	Day 3	Day 15 (±3 days)	Day 29 (±3 days)	Day 30 (±3 days)	Day 31 (±3 days)	Day 8, 21, 36, 43, 50, 64, 71, 78 (±3 days)	Day 57 (±3 days)	Day 85 (±3 days)	Day 113 (±5 days)	
Vital Signs ^j	X	X	X	X	X	X	X	X	X	X	X	X	X	X
Digital Continuous and Triplicate 12-lead ECG ^k	X	X		X	X	X	X				X	X	X	X
Urine Drug Screen ^l ; Cotinine; Alcohol Breath or Urine Test	X	X				X	X			X	X	X	X	X
Study Drug Administration SC Injection			X			X ^m	X							
Adverse Event Monitoring	X	X	X	X	X	X ^m	X	X	X	X	X	X	X	X

Abbreviations: AAT = alpha-1 antitrypsin; BMI = body mass index; ECG = electrocardiogram; ET = early termination; FSH = follicle stimulating hormone; PK = pharmacokinetic; SC = subcutaneous.

^a Screening assessments can occur on multiple days, provided they are within the Day -28 up to Day -2 Screening period.

^b If required per site SOP, admission on Day 14, and/or 28 is acceptable.

^c Negative serum pregnancy test at Screening for WOCBP. Negative highly sensitive urine pregnancy test documented for WOCBP on Day -1 and prior to every dose.

^d FSH only to confirm non-childbearing potential.

^e COVID-19 testing if required per site SOPs.

^f Safety laboratory tests include hematology, clinical chemistry, coagulation and urinalysis as noted in [Table 11](#). Note that for urinalysis, abnormal results on dipstick or urinalysis should lead to laboratory urinalysis testing and/or urine microscopy. Any specific safety labs indicated in [Table 6](#) will be collected according to the schedule in that table. When applicable and feasible, blood sampling should follow evaluations of vital signs and ECGs to reduce any impact on these measurements.

^g Predose plasma PK at every dosing visit. Specific time points for PK and select laboratory Weeks 0 and 4 provided in [Table 6](#). Participants should stay in the clinic for 48 hours after the first and last doses to complete assessments.

- ^h Full physical examination includes (at a minimum): alertness and orientation, general appearance, skin, head, eyes, ears, nose, throat, lungs, cardiovascular, gastrointestinal, musculoskeletal, and neurologic systems. Symptom-directed physical examinations to be performed as necessary.
- ⁱ Height at Screening will be used for BMI calculations at all visits.
- ^j Vital signs will be taken with the participant in the supine position after ≥ 5 minutes of rest. Temperature, respiratory rate, and SpO₂ are measured once per time point. Blood pressure (systolic and diastolic) and pulse: measured ≤ 30 minutes pre-dose and 1 hr (± 10 min), 2 hr (± 10 min), 4 hr (± 20 min), 12 hr (± 1 hr) post dose on Day 1 and once at all other noted visits. Should additional post dose vital signs be collected per Site SOP, these should be captured in eCRF.
- ^k Continuous digital ECG monitoring for at least 48 hours from Day -1 through Day 2 and at least 24 hours through first day of last dose (Day 29); leads may be disconnected for ~ 20 minutes following 24 hours after the first dose to allow for participant cleansing. Additional triplicate 12-lead ECGs are specified in [Table 7](#). Note: only predose triplicate ECGs are required at Day 15. Participant must rest quietly for ≥ 5 minutes prior to triplicate ECGs.
- ^l For drug screen panel, see [Table 11](#) other screening tests.
- ^m Following the second dose (Week 2) all participants will be observed for safety evaluation in the clinic for at least 4 hours post study drug administration or per local SOP (whichever is longer).

Table 6 Plasma PK and Selected Laboratory Time Points (Period 2)

Study Day/Specific Time	Days 1, 15, 29	Days 1 and 29							Days 2 and 30		Days 3 and 31	Weeks 1 through 16
	Pre-dose	Post dose										
	≤ 30 min prior to dose ^b	30 min (± 5 min)	1 hr (± 5 min)	2 hr (± 5 min)	4 hr (± 10 min)	6 hr (± 10 min)	8 hr (± 10 min)	12 hr (± 10 min)	24 hr (± 30 min)	36 hr (± 4 hr)	48 hr (± 4 hr)	Visits 3 through 15
Plasma PK ^a	X	X	X	X	X	X	X	X	X	X	X	Every visit
CBC, CRP, fibrinogen, coagulation, albumin	X					X			X Day 2 only		X Day 3 only	Every visit
Complement	X			X	X	X			X Day 2 only		X Day 3 only	Weeks 1, 5, 6, and 8 only
Cytokines ^c	X			X	X	X			X Day 2 only		X Day 3 only	Weeks 1, 5, 6, and 8 only

Abbreviations: CBC = complete blood count; CRP = C-reactive protein; PK = pharmacokinetic.

^a Sufficient plasma PK sample to cover both WVE-006 and potential metabolites. When applicable and feasible, PK blood sampling should follow evaluations of vital

signs and ECGs to reduce any impact on these measurements.

^b Pre-dose laboratory results are NOT required prior to dosing

^c Cytokines samples will be collected and analyzed for: IL-1 β , IL-6, IL-10, IL-12/23 (P40), IFN- γ , TNF- α , MCP-1, and MIP-1 β

Table 7 Triplicate ECG Assessment Time Points (Period 2)

Study Day/ Specific Time	Day 1			Days 1 and 29							Days 2 and 30	Day 3
	Pre-first dose			Post first and last doses								
	-45 min ±5 min	-30 min ±5 min	-15 min ±5 min	30 min ±5 min	1 hr ±5 min	2 hr ±5 min	4hr ±10 min	6hr ±10 min	8hr ±10 min	12hr ±10 min	24hr ±30 min	48hr ±4 hr
ECG ^a	X	X	X	X	X	X	X	X	X	X	X	X

Abbreviations: ECG = electrocardiogram

^a Digital ECG monitoring for at least 48 hours from Day -1 through Day 2 and at least 24 hours through first day of last dose (Day 29). Additional triplicate ECG measurements at the time points listed here.

